exhibited a pronounced decrease in their measured VO_2 , a pattern which was not present in treated animals which did not experience subsequent hemodynamic instability (**Figure 3**). Having seen this pattern consistently in approximately $n=40$ animal experiments (weight range 2.5-4 kg), we hypothesize that in critically ill patients, VO_2 may decrease below the critical DO_2 and exhibit measureable, even striking, decreases prior to hemodynamic decompensation takes place. If this hypothesis is true, quantification of VO_2 may represent a new 'vital sign' which represents end organ oxygen delivery in critically ill patients. Identification of patients with pathologically supply dependent VO_2 may permit definitive interventions to take place, e.g. initiation of extracorporeal life support, prior to a life-threatening PLOC.

Study Objectives

Specific Aim 1. To demonstrate that oxygen consumption (VO_2) and superior vena cava (SVC) saturations can be safely and precisely measured continuously in newborns undergoing surgery for hypoplastic left heart syndrome (HLHS) or d-transposition of the great arteries with an intact ventricular septum (d-TGA/IVS).

Hypothesis: Measurement of these oxygen-based parameters will not be associated with an increased incidence of equipment-related adverse events (e.g. line displacements, inadvertent extubations) and will lead to precise and reproducible measurements of these important parameters.

Specific Aim 2. To determine whether postoperative loss of circulation (PLOC, defined as cardiac arrest requiring CPR, ECMO cannulation, or causing death) in these patients are associated with a change in oxygen consumption or SVC saturation prior to the event.

Hypothesis: PLOC will be associated with significant decreases in both oxygen consumption and SVC saturations for at least 10 minutes prior to the onset of cardiac arrest.

Specific Aim 3. To determine whether the addition of the oxygen-based measurements to standardly measured parameters (i.e. vital signs, near-infrared spectroscopy

[figure not shown]

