 - Oxygen consumption (Q1 second). The VO_2 will be recorded Q1 second as part of the ventilatory parameters described below.
 - SVC saturations (Q1 second). SVC saturations as determined by oximetry will be recorded Q1 second.
- Standard of care monitoring
 - Vital signs. These data will include heart rate, arterial blood pressures, respiratory rate, pulse oximetry, atrial pressures, and central venous pressure. As discussed in detail below, these data will be extracted from an existing program which records the primary data Q5 second in time stamped fashion (T3 Program, Arcardia Solutions).
 - *NIRS*. The near-infrared spectroscopy value represents the oxyhemoglobin saturation of the deep tissues. This will be recorded Q1 second in time-stamped fashion.
 - *Ventilatory parameters*. All ventilation parameters will be recorded from the spirometry recordings from the capnograph. These data include end-tidal CO_2 , fraction of inspired CO_2 , respiratory rate, fraction of inspired O_2 , fraction of expired O_2 , peak end expiratory pressure, peak inspiratory pressure, plateau pressure, mean airway pressure, airway resistance, inspiratory-expiratory time ratio, inspiratory and expiratory times, inspiratory and expiratory tidal volume, compliance of the respiratory system, minute ventilation, VCO_2 , energy expenditure, and respiratory quotient. These data will be recorded Q1 second in time-stamped fashion.
- *Standard labs* will be drawn at the treating team's discretion and gathered from the medical record each day.
 - Arterial blood gas and time drawn
 - Serum lactate and time drawn
 - SVC (or other venous) saturations and time drawn
 - Chemistry profile, complete blood count (white blood cell count, hemoglobin, hematocrit and platelet count), coagulation profile and times drawn
- Treatments
 - *Inotrope infusions* are routinely administered, often in high doses, to these patients in the perioperative setting. It is thought that these infusions affect both oxygen delivery to all tissues, as well as increasing myocardial oxygen consumption.
 - Additionally, we will record *intermittently administered medications*, such as epinephrine, calcium gluconate, sodium bicarbonate, hydrocortisone, and

- thyroid replacement therapy, all of which may affect oxygen consumption and oxygen delivery as well.

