- Chest explorations and operative interventions performed at the bedside (e.g. clipping of BTS or Sano shunt) will be recorded each day from a review of the medical record, discussion with the primary team (including the bedside nurse) and the notes within the medical record.
 - Blood loss from chest tubes (in mL/kg each hour) and blood product administrations (including the blood products given and the times at which they are given) will be recorded from the medical record each day.
 - Sedatives and paralytics are routinely used and also affect oxygen consumption.
 - Diuretic medications are also routinely used, can affect preload.
 - Arrhythmias and
 - Other clinical parameters
 - Urine output is a crude marker of intravascular volume and end organ oxygen delivery.
 - The presence of enteral feedings, the rate of feedings and the caloric densities will also be recorded, as these may affect a patient's systemic vascular resistance.
 - Operative characteristics
 - Full preoperative and postoperative anatomic diagnoses
 - Residual anatomic defects
 - Total pump time, cross-clamp time, circulatory arrest time, regional perfusion time, minutes of continuous and modified ultrafiltration, blood products administered on bypass

Data Collection Methods, Assessments and Schedule

Outcome measurements

The majority of the endpoints presented above are routinely collected within the medical record as a part of patient care. Therefore, the majority of the data will be abstracted directly from the medical record and into a spreadsheet for data analysis by a member of the study team during each day for the duration of the study. The PI employs two full-time technicians within his lab who will assist with this labor intensive process.

- The oxygen-based measurements which are central to this study, including VO_2 , SVC saturation, as well as all ventilatory parameters listed above will be saved to a computer program (S5 Collect, GE Healthcare) attached to the patient's monitor. This program saves data in time stamped fashion Q1 second.
- Time-stamped vital sign data listed above will be exported daily from the hospital's in situ T3 program (Arcadia Solutions).
- The labs, treatments and other clinical parameters (see previous section) will be extracted in time-stamped fashion from the medical record each day by a member of the study team.

Patient variables

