Quality in the data collected by the oxygen consumption monitor will be ensured by a self-test at startup according to the manufacturer's instructions. Further, anesthesiologist and respiratory care staff will be instructed to monitor for the degree of air leak from the respiratory system by calculating the difference between inspiratory and expiratory measured tidal volumes. If the airleak exceeds this value, air may be added to the tracheal tube cuff. We have shown that when this difference is <15%, VO_2 data are accurately measured in newborns.²⁴ Further, an absence of end-tidal CO_2 data will be used as a signal of an endotracheal tube disconnection and possible suctioning event. VO_2 measurements are known to be unstable for several minutes following suctioning²⁸, so we will exclude VO_2 data for 10 minutes following any ETT disconnect from analyses.

Figure 6. The oxygen-based monitoring and data collection systems utilized for this study are attached to a rolling pole which can be placed anywhere around the patient and easily moved for convenience and safety.

Data within the SVC monitoring probe will be ensured by an in vitro calibration prior to probe insertion. When ever the treating team sends a venous blood gas from the central venous line, the co-oximetry value will be entered into the machine and used to recalibrate the probe in real-time.

Quality in the transfer of data from the medical record to the spreadsheet will be ensured by an independent review of the primary data by a second member of the study team. Furthermore, when possible, the fields for data entry will contain 'Data Validation' functions (i.e. value will turn red if outside expected limits, and hard stops will be inserted for physiologically impossible values). Additionally, drop down lists will be utilized when possible to minimize data entry errors.

Data Analysis Plan

Patients will be divided into patients who do and do not experience PLOC. All variables will be normalized to hours prior to bypass, bypass time and hours post-bypass time, such that all data for a specific post-bypass time will be aligned between patients. All weight-dependent variables will be normalized to preoperative body weight. Using GraphPad Prism, each variable will be entered into a different column for analysis.

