Simple analyses (e.g. mean, standard deviation, tests for normality) will be completed within GraphPad. With regards to the primary endpoint, VO₂ measurements will be analyzed for 120 minutes prior to a PLOC event in cases, and a randomly selected 120 minute period in controls. Values will be compared between cases and controls using generalized estimating equations (GEEs) to account for the correlation of multiple measurements within the same patient and to compare means between cases and controls. A post-hoc broken stick analysis will be used to determine the time prior to the event at which the VO₂ changed in each patient experiencing an event. Data for HLHS and dTGA patients will be pooled together.

More complex analyses will be completed by a collaborating company called Etiometry (including [name] and [name], co-investigators on this study), with whom the PI and others within the CICU have an established relationship. Deidentified information will be sent to the company, who will complete further analyses.

Power Calculations and Sample Size

The measured oxygen consumption in neonates following S1P has been described as 86 ± 16 mL/min/m^{2.22}. A sample size that includes 3 cardiac arrest events would allow us to detect a true decrease of 53 mL/min/m² in oxygen consumption with 90% power and a significance level of 0.05 (two tailed). Based on the significant change in VO₂ noted in the animal studies preceding cardiac arrest, we do not feel that this number is an unreasonable number. In order to collect 3 patients meeting the endpoint, we predict that we will require 20 patients undergoing S1P.

Risks and Discomforts

Because this is a prospective, observational study which we do not expect to change the standard of care, the risks associated with this study are really those of the standard

of care. The VO_2 measurements will be taken using an FDA-approved device which samples gas from the side of the tracheal tube of each patient. In reality, the adapter used by the study monitor is smaller and lighter than than used in our current capnographs, so the risk of accidental endotracheal tube removal should be the same or lower.

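### The disconnect rule rests on absent end-tidal CO2 alone, so in an occasional case it could delete the last VO2 minutes before PLOC

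*Combined protocol and SAP*

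**What the plan says.** Data Management and Statistical Analysis, Quality control methods: missing end-tidal CO2 data "will be used as a signal of an endotracheal tube disconnection and possible suctioning event". VO2 is described as unstable for several minutes after suctioning, "so we will exclude VO_2 data for 10 minutes following any ETT disconnect from analyses". The section gives no second criterion, minimum duration, review of flagged gaps, or analysis without the exclusion.

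Data Analysis Plan: VO2 "measurements will be analyzed for 120 minutes prior to a PLOC event in cases, and a randomly selected 120 minute period in controls". Means are compared by GEE, and a post-hoc broken-stick fit dates the change in each infant with an event.

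Study Objectives, Specific Aim 2: the event is "PLOC, defined as cardiac arrest requiring CPR, ECMO cannulation, or causing death", and the hypothesis is a fall lasting "for at least 10 minutes prior to the onset of cardiac arrest". Neither this section nor Endpoints/Outcomes says which moment is the event time.

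Secondary Outcomes, Ventilatory parameters: the recorded signals include "peak end expiratory pressure, peak inspiratory pressure, plateau pressure, mean airway pressure", inspiratory and expiratory tidal volumes, and inspired and expired O2 fractions. Data Collection Methods says of S5 Collect, which holds these with VO2: "This program saves data in time stamped fashion Q1 second". The disconnect rule uses none of them.

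**The concern.** A CO2 reading at the airway needs a connected tube, a working gas sample and blood flow through the lungs. The rule attributes its absence to the tube alone. In S1P infants lung flow comes through a surgical shunt (Figure 2 caption), and the endpoint is loss of circulation, so the CO2 signal can be lost through the process under study.

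If that happens before the recorded event, VO2 goes missing for a reason tied to the outcome. Controls would lose mainly true disconnects, while a case could also lose low-flow minutes close to the event. The likely direction is toward understating a late fall. Changing the length of the exclusion would not cure this, because the fault lies in what starts it. Suctioning is not among the items listed for recording, so no planned bedside record would settle what a given gap was.

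**Working it through.** **Inputs.** Exclusion of 10 minutes (Quality control methods); window of 120 minutes (Data Analysis Plan); VO2 every second (Data Collection Methods); 3 events, SD 16 and a detectable fall of 53 mL/min/m2 (Power Calculations and Sample Size).

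**The plan's own figure.** Taking 3 controls against the 3 cases (the control number is my assumption), (t[0.975, 4 df] + z[0.90]) × 16 × √(2/3) = 53.01, which matches 53. This point does not alter that figure. I use 53 only as the size of an illustrative fall.

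**Which minutes go.** Count the 10 minutes forward from the moment CO2 is lost (assumption), m minutes before the event:

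- m = 0: nothing is removed from the pre-event window.
- m up to 10: the last m minutes are removed.
- m from 10 to 20: 20 − m of the last 10 minutes are removed. At m = 15 that is 5.
- m of 20 or more: none of the last 10 minutes is removed.

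**Most that one trigger removes.** 600 of 7,200 values = 10/120 = 8.3% of that case's window. Across 3 cases: 10/360 = 2.8% of case minutes.

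**Effect on that case's contrast.** Assume VO2 drops by a step of 53 for the last T minutes and the last 10 minutes are deleted (T of 10 or more). Full data give 53 × T/120; after deletion, 53 × (T − 10)/110.

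| T (min) | Full | After deletion | Lost |
|---|---|---|---|
| 10 | 4.4 | 0 | 100% |
| 20 | 8.8 | 4.8 | 45% |
| 30 | 13.3 | 9.6 | 27% |
| 60 | 26.5 | 24.1 | 9% |
| 120 | 53 | 53 | 0% |

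If only the last 5 minutes are deleted, the 10-minute fall gives 53 × 5/115 = 2.3 and the 30-minute fall 53 × 25/115 = 11.5.

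**Effect on the group.** Weight 3 cases equally, with the same fall in each and one affected. For T = 10 the contrast is (4.42 + 4.42 + 0)/3 = 2.9 instead of 4.4. For T = 30 it is (13.25 + 13.25 + 9.64)/3 = 12.0 instead of 13.3.

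**Broken-stick fit.** With T = 10 and the last 10 minutes gone, no data remain after the break, so it cannot be found in that infant. If VO2 instead falls in a straight line by 53 over 30 minutes, the deepest fall left in the data is 53 × 20/30 = 35.3.

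**The case against.** The strongest reply is that the rule rarely bites and protects data quality when it does.

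- **Only absent data count.** A low or falling CO2 value that is still recorded triggers nothing. This stands.
- **The exclusion runs forward.** Flow low enough to abolish expired CO2 is likely to be close to PLOC, so most deleted minutes would lie after the event. This largely stands. End-tidal CO2 is also displayed to clinicians throughout (Study Treatments, VO2 monitoring), so a long silent absence before CPR is hard to picture. But if cannulation or death sets the event time, low-flow minutes could fall inside the window.
- **Absent CO2 is also a validity check.** The background section on oxygen consumption says O2 and CO2 are both measured by side-stream sampling, while a pneumotachometer measures volume and flow. A sampling failure would lose CO2 with pressure and volume preserved, and VO2 would then be invalid. This stands, and any replacement rule must deal with it.
- **VO2 at that moment may be the event itself** rather than a precursor. This is arguable, but it is better judged on retained, flagged data than settled by deletion.

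A reader might infer that one affected infant costs a third of the case data. It is one of three cases, but at most 2.8% of case minutes. A reader might also infer that any trigger 10 or more minutes ahead erases Aim 2's 10 minutes. All of them go only when it comes about 10 minutes before the event. Nor does the plan specify a separate 10-minute analysis; that figure is hypothesis wording.

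**Conclusion.** The concern holds in a limited form. The trigger is not specific to a disconnect, and in an occasional case it could remove the final pre-event VO2 for a reason linked to the outcome. The damage to that case's contrast runs from none (loss at the event, or a fall across the whole window) to complete (a 10-minute fall with the signal lost 10 minutes ahead).

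This rests on three things outside the documents: the physiological link between lung flow and expired CO2, a CO2 loss that precedes the PLOC time stamp, and the illustrative step fall. The documents give no frequency for such gaps. They therefore do not support the stronger conclusion, which a reader might draw, that the Aim 2 comparison is generally biased toward no change. With about 3 events expected and the needed signals already stored, the rule is still worth tightening before the data are cleaned.

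**What to change.** In Quality control methods, change the data-cleaning rule as follows:

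1. Call a gap a disconnect only when absent end-tidal CO2 is accompanied by loss of airway pressure or expired tidal volume. Start the 10-minute exclusion then.
2. Where pressure and volume continue, keep VO2 only if inspired and expired O2 readings are also present and plausible, and flag those minutes as possible low flow. Otherwise exclude them as a gas-sampling failure.
3. Classify gaps without knowledge of case status.
4. Report excluded minutes separately for cases and controls.
5. Repeat the primary comparison under the plan's present CO2-only rule.

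This needs no new measurements and changes nothing in patient care. The cost is a few sentences, a little more programming, and some retained minutes whose VO2 quality is less certain. Step 5 shows whether those minutes matter.

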Serum lactate represents the biproduct of anaerobic respiration within the tissues, and is therefore an obvious choice as a marker of inadequate DO_2 . It is commonly measured in the clinical management of neonates following congenital heart surgery. Unfortunately, serum lactate can be falsely low in extreme tissue malperfusion (it is thought that lactate does not equilibrate with the plasma in situations of extremely low DO_2), and can be falsely elevated by the use of inotropes (prototypically, epinephrine) and in hepatic dysfunction. Together, these factors make isolated measurements of lactate difficult to interpret.

It has been previously shown that in adults experiencing a cardiac arrest, a high serum lactate (>10 mg/dL) is more common in patients experiencing a recurrent cardiac arrest.¹³ It is also known that serum lactate measurements may correlate with chances of survival following cardiopulmonary bypass in neonates.¹⁴ On a population level, it is

known that patients who experience a die following a postoperative cardiac arrest have higher pre-arrest lactate levels than those who survive.¹⁵ However, to date, this information has been of limited prospective utility in the prospective management of patients, specifically in guiding therapies to optimize DO_2 .^{16,17}

Oxygen consumption

As discussed above, when DO_2 decreases below the critical DO_2 threshold, VO_2 becomes pathologically supply dependent. In clinical practice, VO_2 is most commonly estimated based on normal values, though this has been shown to be an inaccurate practice.¹⁸ Alternatively, VO_2 can be measured in intubated patients by calculating the fraction of oxygen that is inspired versus that which is expired during each breath. That information, combined with the volume of each breath, represents the volume of oxygen consumed by the patient.

Several commercially available devices have been shown to exhibit both precision and accuracy in quantifying VO_2 in newborns, even those following congenital heart surgery. For example, Li has described the VO_2 of newborns following S1P to be ~80-100 mL/min/m² ¹⁹, using a VO_2 monitor which utilizes mass spectroscopic evaluation of inhaled versus exhaled gases. However, none of these studies have attempted to correlate VO_2 with outcomes, neither short- nor long-term, including PLOC.¹⁹⁻²³

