Members of this research team have become familiar with another device used to quantify VO_2 , and have utilized it in several clinical studies to date.^{24,25} Over the past three years, for example, members of our group completed a study in which VO_2 and VCO_2 were quantified in postoperative Fontan patients using this device in the CICU.²⁴ The nursing and respiratory care staff are therefore already familiar with the machine and its use.

The device utilizes an in-line adapter which affixes to the end of the endotracheal tube, and samples gas concentrations on a breath-to-breath basis (GE Healthcare, E-CAIOVX module, Waukesha, WI). The process for gas exchange measurement has been described previously.²⁶ In brief, inspiratory and expiratory gas concentrations are obtained every breath utilizing a fast differential paramagnetic O_2 analyzer and infrared CO_2 analyzer by side-stream sampling. A fixed orifice, pressure differential pneumotachometer (D-lite (+) or Pedi-lite (+), GE Healthcare, Madison, WI) is used to measure gas volumes and flows and to calculate VO_2 . This device has been well validated against mass spectrometry and has been found to be both accurate and precise at even low VO_2 levels.²⁶

Preliminary Studies

The impetus for this study has stemmed from pre-clinical work performed by the PI. In other work, the PI studied an intravenous treatment for complete asphyxia in which oxygen gas is packaged into microparticles to be rendered injectable.²⁷ In this model, oxygen consumption was quantified using the GE device. We have noticed that animals with extreme, untreated asphyxia exhibited a lower VO_2 when compared to their healthy baseline, and that prior to a subsequent cardiac arrest, many animals

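### VO2 recorded just after a change in inspired oxygen is neither excluded nor flagged; one step barely moves the 120-minute mean but can mislead the broken-stick timing and the 10-minute Aim 2 claim

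*Combined protocol and SAP*

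**What the plan says.** The Background section on oxygen consumption says VO2 is obtained at the airway by "calculating the fraction of oxygen that is inspired versus that which is expired during each breath", combined with the volume of each breath.

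Quality control methods gives these safeguards for VO2:

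- a start-up self-test;
- a leak check made by "calculating the difference between inspiratory and expiratory measured tidal volumes", with accuracy claimed when the difference is below 15%;
- an exclusion. VO2 "measurements are known to be unstable for several minutes following suctioning", so the plan removes VO2 "data for 10 minutes following any ETT disconnect from analyses". Missing end-tidal CO2 is the signal for a disconnect.

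The ventilatory parameters listed under Secondary Outcomes include "respiratory rate, fraction of inspired" O2, stored every second with time stamps. The same list ends with "energy expenditure, and respiratory quotient".

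The Data Analysis Plan compares VO2 by GEE between the 120 minutes before PLOC in cases and a random 120-minute period in controls. A post-hoc broken-stick analysis then dates the VO2 change in each case. The Aim 2 hypothesis is a fall lasting at least 10 minutes before arrest. No section screens, adjusts for or matches on inspired oxygen.

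**The concern.** Airway uptake equals tissue consumption only while the oxygen held in the lungs is constant. When the inspired fraction is raised, the lungs take up extra oxygen that the device counts as consumed. When it is lowered, stored oxygen leaves and is subtracted. The existing exclusion cannot catch this, because a change in inspired oxygen leaves end-tidal CO2 present. The plan already accepts that VO2 should be set aside while unsettled, but applies this to one trigger only.

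An upward step before an event could cover a real fall, and a downward step could look like one. The plan expects about 3 events, so one distorted trace is a third of the evidence on when VO2 changes.

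**Working it through.** **The plan's own figure.** Power Calculations gives mean 86, SD 16, 3 events, a detectable fall of 53 mL/min/m2, 90% power and two-sided 0.05, without naming a formula. Taking 3 versus 3 with a t critical value (4 df) and a normal quantile for power: (2.776 + 1.282) x 16 x sqrt(2/3) = 53.01. The figure reproduces.

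**Assumptions not in the documents.** Weight 3 kg, surface area 0.20 m2, lung gas 20-30 mL/kg (60-90 mL), one step of 0.2-0.6 in inspired fraction. VO2 is then 86 x 0.20 = 17.2 mL/min.

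**Oxygen moved by one step.** Lung gas volume x change in fraction: 60 x 0.2 = 12 mL to 90 x 0.6 = 54 mL, which is 0.7-3.1 minutes of VO2.

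**Shift in mean VO2** = oxygen moved / (minutes x 0.20):

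| Averaging period | Shift, mL/min/m2 | Share of 86 |
|---|---|---|
| 120 min | 0.5-2.3 | 0.6-2.6% |
| 10 min | 6-27 | 7-31% |
| 3 min | 20-90 | 23-105% |

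With wider assumptions (3.3 kg, 0.21 m2, 15-35 mL/kg, step 0.1-0.6) the oxygen moved is 5-69 mL. The shift is 0.2-2.8 over 120 minutes and 2.4-33 over 10 minutes.

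**Several steps.** With constant lung gas volume and no minutes dropped, the total over a window is lung volume x (final minus initial fraction), because intermediate steps cancel. Even a net move from 0.21 to 1.00 gives 90 x 0.79 / (120 x 0.20) = 3.0 mL/min/m2.

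**Effect on the primary comparison.** In the formula above, if every case's fall of 53 is masked by 2.25, power is Phi((53 - 2.25)/13.06 - 2.776) = 0.87, against 0.90. Masking by 2.75 gives 0.86.

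**Effect on the broken stick.** As an illustration, take a noise-free trace of one-minute values at 86 until 30 minutes before the event, then falling in a straight line to 33. Add an upward step of 0.4 with 75 mL of lung gas: 75 x 0.4 = 30 mL, spread over 3 minutes, or 50 mL/min/m2 in each. Least-squares two-segment fits, with the break searched on a half-minute grid, give:

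| Step placed (min before event) | Fitted break (true 30) |
|---|---|
| 60 | 32.5 |
| 40 | 35 |
| 25 | 23.5 |
| 15 | 13.5 |
| 10 | 31 |
| 5 | 34.5 |

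The error runs from 1 to 16.5 minutes, depending on where the step falls. If the true break is at 10 minutes, a downward step of the same size placed at 15 minutes moves the fitted break to 21 minutes. With only 12 mL moved upward (true break 30), the error is 0.5-5.5 minutes.

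**Steady high inspired oxygen.** Uptake equals consumption here, so only measurement error is in question. If the device uses nitrogen balance (not stated), VO2/VE = FiO2(1 - FeO2 - FeCO2)/(1 - FiO2) - FeO2. With FeCO2 0.035 and VO2/VE 0.04, a 0.001 error in FiO2 alone changes VO2 by 3.6% at 0.30 and 25.4% at 0.90. The same error shared by both oxygen readings largely cancels, leaving about 0.1% at 0.90: (0.001/0.10) x 0.005 / 0.04. The documents do not show which case applies.

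**The case against.** The strongest reply is that the primary comparison uses 120-minute means, and one step moves those by about 2 mL/min/m2 or less. That stands. A reader might infer that the main case-control result is compromised; the arithmetic does not support it.

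A reader might also infer that VO2 is invalid whenever inspired oxygen is high. At a steady fraction it is not. Amplified instrument error is possible, but its size depends on an algorithm and limits that the documents do not give.

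A third tempting inference is that infants nearing PLOC have more oxygen changes than controls. That is plausible, but no section reports how inspired oxygen is managed or how often it changes.

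It can also be said that no 10-minute mean is planned, that the broken stick is labelled post hoc, and that the disconnect rule already removes oxygen changes made around suctioning. Each is true. They limit the point but do not remove it: the broken stick is a named analysis, Aim 2 states a 10-minute duration, and changes made away from a disconnect stay in.

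The statement that the device "has been found to be both accurate and precise at even low" VO2 levels does not answer the point. It gives no inspired-oxygen range, and an accurate reading of airway uptake still differs from tissue consumption while lung oxygen is changing.

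**Conclusion.** The point holds for timing and short-duration findings, not for the 120-minute mean. Under the stated assumptions one step shifts the 120-minute mean by 0.5-2.3 mL/min/m2, a 10-minute average by 6-27, and minute-level values by more. In the illustration it misdated the change by 1 to 16.5 minutes. The direction depends on the step: upward masks a fall, downward imitates one. The mechanism follows from gas balance. The sizes rest on assumed weight, surface area, lung volume and step. How often steps occur, and whether cases and controls differ, is unknown until the recorded signal is tabulated.

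**What to change.** Add a paragraph to Quality control methods and the Data Analysis Plan:

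- Flag VO2 for a short washout period after a step change in recorded inspired oxygen. Fix the step threshold and the washout length before the traces are examined.
- Flag VO2 above any inspired-oxygen limit in the device specification, and cite that limit.
- Run the broken-stick analysis and the GEE comparison with and without flagged minutes, and report both. Do not bar a conclusion automatically because it rests on one version.
- Report inspired oxygen and the share of minutes flagged in case and control windows. This tests whether the groups differ.

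Do not screen on respiratory quotient. VO2 is its denominator: with VCO2 unchanged and an assumed quotient of 0.85, the planned fall from 86 to 33 would raise it to 0.85 x 86/33 = 2.2, so the filter could flag the very signal the study seeks.

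The cost is a paragraph and some analysis code, with no new data. The drawback is fewer usable minutes in the sensitivity version, which matters with about 3 cases and is why both versions are shown. No change to clinical oxygen management is implied.
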